9.2.7 Visit 8 (76 weeks)

Visit 8 will take place 28 weeks after Visit 7 (76 weeks after Visit 1). A visit window of ± 7 days from the scheduled visit date is permitted, but it is preferred that the visit is performed on the scheduled visit day where possible.

The following assessments will be made: vital signs, physical examination (including height and body weight), ECG, C-SSRS, Vineland-II, QOLCE/QOLIE, S/CGIC and S/CGICSD. Clinical laboratory samples (urine [where possible] and blood) will be taken for hematology, biochemistry and urinalysis. The patient's IVRS report and paper diary will be reviewed and the information recorded along with information regarding AEs, IMP, epilepsy-related hospitalizations, concomitant medications and/or changes to medication. The Investigator must assess adherence to the dosing regimen.

A 14-week supply of IMP will be issued to the patient/caregiver.

Following Visit 8, safety telephone calls must be made every 4 weeks (± 7 days) to assess AEs, epilepsy-related hospitalizations, concomitant medications and/or changes to medication. In addition, during titration of doses above 20 mg/kg/day, safety telephone calls must be made every 7 days (± 3 days) until stable dosing is achieved.

At least 1 dispensing appointment will be scheduled to occur between Visit 8 and Visit 9. The dispensing appointment date(s) will be calculated from Visit 8. At each dispensing appointment caregivers will be dispensed with sufficient IMP to be administered until the next scheduled appointment. Patients need not attend the dispensing appointments.

9.2.8 Visit 9 (104 weeks)

Visit 9 will take place 28 weeks after Visit 8 (104 weeks after Visit 1). A visit window of ± 7 days from the scheduled visit date is permitted, but it is preferred that the visit is performed on the scheduled visit day where possible.

The following assessments will be made: vital signs, physical examination (including height and body weight), effects on menstruation cycles (for females), Tanner Staging (for patients aged 10–17 [inclusive], or earlier if clinically indicated by onset of menarche or other signs of precocious puberty), ECG, C-SSRS, Vineland-II, cognitive assessment battery (participating centers only), QOLCE/QOLIE, S/CGIC and S/CGICSD. Clinical laboratory samples (urine [where possible] and blood) will be taken for determination of serum IGF-1 levels (for patients less than 18 years of age), pregnancy (if appropriate, using a serum sample), hematology, biochemistry and urinalysis. The patient's IVRS report and paper diary will be reviewed and the information recorded along with information regarding AEs, IMP, epilepsy-related hospitalizations, concomitant medications and/or changes to medication. The Investigator must assess adherence to the dosing regimen.

The cognitive assessment battery will only be administered at a sub-group of centers that have the expertise to conduct the assessments (ideally before any other study procedures but can be completed on a separate day, if necessary, within 3 days of the visit) and will only be administered to patients who underwent cognitive testing during their Core Study.

A 14-week supply of IMP will be issued to the patient/caregiver.

Following Visit 9, safety telephone calls must be made every 4 weeks (± 7 days) to assess AEs, epilepsy-related hospitalizations, concomitant medications and/or changes to medication. In addition, during titration of doses above 20 mg/kg/day, safety telephone calls must be made every 7 days (± 3 days) until stable dosing is achieved.

At least 1 dispensing appointment will be scheduled to occur between Visits 9 and 10. The dispensing appointment date(s) will be calculated from Visit 9. At each dispensing appointment caregivers will be dispensed with sufficient IMP to be

administered until the next scheduled appointment. Patients need not attend the dispensing appointments.

9.2.9 Visit 10 (132 weeks)

Visit 10 will take place 28 weeks after Visit 9 (132 weeks after Visit 1). A visit window of ± 7 days from the scheduled visit date is permitted, but it is preferred that the visit is performed on the scheduled visit day where possible.

The following assessments will be made: vital signs, physical examination (including height and body weight), ECG, C-SSRS, Vineland-II, QOLCE/QOLIE, S/CGIC and S/CGICSD. Clinical laboratory samples (urine [where possible] and blood) will be taken for hematology, biochemistry and urinalysis. The patient's IVRS report and paper diary will be reviewed and the information recorded along with information regarding AEs, IMP, epilepsy-related hospitalizations, concomitant medications and/or changes to medication. The Investigator must assess adherence to the dosing regimen.

A 14-week supply of IMP will be issued to the patient/caregiver.

Following Visit 10, safety telephone calls must be made every 4 weeks (± 7 days) to assess AEs, epilepsy-related hospitalizations, concomitant medications and/or changes to medication. In addition, during titration of doses above 20 mg/kg/day, safety telephone calls must be made every 7 days (± 3 days) until stable dosing is achieved.

At least 1 dispensing appointment will be scheduled to occur between Visit 10 and 'End of Treatment' visit. The dispensing appointment date(s) will be calculated from Visit 10. At each dispensing appointment caregivers will be dispensed with sufficient IMP to be administered until the next scheduled appointment. Patients need not attend the dispensing appointments.

9.2.10 Visit 11 (156 weeks)

Visit 11 will take place 24 weeks after Visit 10 (156 weeks after Visit 1). A visit window of ± 7 days from the scheduled visit date is permitted, but it is preferred that the visit is performed on the scheduled visit day where possible.

The following assessments will be made: vital signs, physical examination (including height and body weight), effects on menstruation cycles (for females), Tanner Staging (for patients aged 10–17 [inclusive], or earlier if clinically indicated by onset of menarche or other signs of precocious puberty), ECG, C-SSRS, Vineland-II, cognitive assessment battery (participating centers only), QOLCE/QOLIE, S/CGIC and

S/CGICSD. Clinical laboratory samples (urine [where possible] and blood) will be taken for determination of serum IGF-1 levels (for patients less than 18 years of age), pregnancy (if appropriate, using a serum sample), hematology, biochemistry and urinalysis. The patient's IVRS report and paper diary will be reviewed and the information recorded along with information regarding AEs, IMP, epilepsy-related hospitalizations, concomitant medications and/or changes to medication. The Investigator must assess adherence to the dosing regimen.

The cognitive assessment battery will only be administered at a sub-group of centers that have the expertise to conduct the assessments (ideally before any other study procedures but can be completed on a separate day, if necessary, within 3 days of the visit) and will only be administered to patients who underwent cognitive testing during their Core Study.

A 14-week supply of IMP will be issued to the patient/caregiver.

Following Visit 11, safety telephone calls must be made every 4 weeks (± 7 days) to assess AEs, epilepsy-related hospitalizations, concomitant medications and/or changes to medication. In addition, during titration of doses above 20 mg/kg/day, safety telephone calls must be made every 7 days (± 3 days) until stable dosing is achieved.

At least 1 dispensing appointment will be scheduled to occur between Visits 11 and 12. The dispensing appointment date(s) will be calculated from Visit 11. At each dispensing appointment caregivers will be dispensed with sufficient IMP to be administered until the next scheduled appointment. Patients need not attend the dispensing appointments.

9.2.11 Visit 12 (184 weeks)

Visit 12 will take place 28 weeks after Visit 11 (184 weeks after Visit 1). A visit window of ± 7 days from the scheduled visit date is permitted, but it is preferred that the visit is performed on the scheduled visit day where possible.

The following assessments will be made: vital signs, physical examination (including height and body weight), ECG, C-SSRS, Vineland-II, QOLCE/QOLIE, S/CGIC and S/CGICSD. Clinical laboratory samples (urine [where possible] and blood) will be taken for hematology, biochemistry and urinalysis. The patient's IVRS report and paper diary will be reviewed and the information recorded along with information regarding AEs, IMP, epilepsy-related hospitalizations, concomitant medications and/or changes to medication. The Investigator must assess adherence to the dosing regimen.

A 14-week supply of IMP will be issued to the patient/caregiver.

Following Visit 12, safety telephone calls must be made every 4 weeks (± 7 days) to assess AEs, epilepsy-related hospitalizations, concomitant medications and/or changes to medication. In addition, during titration of doses above 20 mg/kg/day, safety telephone calls must be made every 7 days (± 3 days) until stable dosing is achieved.

At least 1 dispensing appointment will be scheduled to occur between Visit 12 and 'End of Treatment' visit. The dispensing appointment date(s) will be calculated from Visit 12. At each dispensing appointment caregivers will be dispensed with sufficient IMP to be administered until the next scheduled appointment. Patients need not attend the dispensing appointments.

9.2.12 End of Treatment/Withdrawal Visit

This visit will take place after a maximum of 4 years' (208 weeks after Visit 1) treatment (as detailed below), or following early withdrawal from the study.

- A patient with at least 2 years' participation in the OLE (≥ 104 weeks after Visit 1) will complete the OLE phase when GWP42003-P is approved in their indication and is commercially available. Patients will complete an unscheduled 'End of Treatment' visit to transition from OLE to commercial product. The timing will vary per patient and is projected to begin in February 2019.
- A patient with less than 2 years' participation in the OLE when GWP42003-P is approved in their indication and is commercially available will continue the OLE phase until reaching a maximum of 2 years' OLE treatment, at which point an unscheduled 'End of Treatment' visit will be conducted. The unscheduled 'End of Treatment' visit will be conducted no earlier than 730 days after Visit 1.
- Patients who do not continue treatment with GWP42003-P will be scheduled for an 'End of Taper' visit.

The following assessments will be made at the 'End of Treatment'/Withdrawal visit: vital signs, physical examination (including height and body weight), effects on menstruation cycles (for females), Tanner Staging (for patients aged 10–17 [inclusive], or earlier if clinically indicated by onset of menarche or other signs of precocious puberty), ECG, C-SSRS, Vineland-II, cognitive assessment battery (participating centers only), QOLCE/QOLIE, S/CGIC and S/CGICSD. Clinical laboratory samples (blood and urine [where possible]) will be taken for determination of serum IGF-1 levels (for patients less than 18 years of age), hematology,

biochemistry, a pregnancy test (if appropriate, using a serum sample) and urinalysis. The patient's IVRS report and paper diary will be reviewed and the information recorded along with information regarding AEs, IMP, epilepsy-related hospitalizations, concomitant medications and/or changes to medication. The Investigator must assess adherence to the dosing regimen.

The cognitive assessment battery items will only be administered at a sub-group of centers that have the expertise to conduct the assessments (ideally before any other study procedures but can be completed on a separate day, if necessary, within 3 days of the visit) and will only be administered to patients who underwent cognitive testing during their Core Study.

All IMP (used and unused) will be collected and a check of the returned IMP against usage should be made. For patients who withdraw early or who do not transition to commercial product, the IVRS will be contacted to confirm withdrawal from the study. For patients who immediately continue to use GWP42003-P following the 'End of Treatment' visit, the IVRS will be contacted to confirm the patient's completion of this study and the paper diaries will be collected. For patients 12 years of age and older, the trained Investigator or study coordinator will complete the Study Medication Use and Behavior Survey as an interview with the patient/caregiver.

For patients who do not immediately continue to use GWP42003-P following the 'End of Treatment' visit, IMP will be down-titrated at home (10% per day for 10 days). Additional IMP will be dispensed, if required. Patients who withdraw early should also begin the taper period following the Withdrawal visit (unless continued dosing is not possible due to an AE). The IVRS will generate the patient's daily IMP dosing volumes for the 10-day taper period, during which time diary information will continue to be recorded in the paper diary.

Following the 'End of Treatment'/Withdrawal visit, the IVRS seizure reporting diary should only be completed on the day before the 'End of Taper Period' visit and on the day before the Follow-up visit.

9.2.13 End of Taper Period Visit

This visit will take place 10 (+ 3) days after the 'End of Treatment' visit or Withdrawal visit for patients who withdraw early or who do not transition to commercial product. For patients who begin to taper IMP but subsequently withdraw/do not complete the full taper period, this visit should occur on the final day of dosing or as soon as possible after this date.

The following assessments will be made: vital signs, physical examination (including height and body weight), CWS/PCWS and C-SSRS. In addition, the following assessments will be made for patients who do not transition to commercial product or withdraw early and taper IMP (including withdrawal during the taper period): ECG and clinical laboratory samples (blood and urine for hematology, biochemistry and urinalysis). The patient's IVRS report and paper diary will be reviewed and the information recorded along with information regarding AEs, IMP, epilepsy-related hospitalizations, concomitant medications and/or changes to medication. The Investigator must assess adherence to the dosing regimen.

All IMP (used and unused) will be collected and a check of the returned IMP against usage should be made. For patients 12 years of age and older, the trained Investigator or study coordinator will complete the Study Medication Use and Behavior Survey as an interview with the patient/caregiver.

Following the 'End of Taper Period' visit (or date of final dosing), the IVRS seizure reporting diary should only be completed on the day before the Follow-up visit.

9.2.14 Post-Taper Safety Telephone Call

A safety telephone call must be made 2 weeks (\pm 3 days) after the 'End of Taper Period' visit or date of final dosing. Patients or their caregivers will be asked for information on AEs, epilepsy-related hospitalizations, concomitant medications and/or changes to medication. The CWS/PCWS will be administered as well.

Following this call, the IVRS seizure reporting diary should only be completed on the day before the Follow-up visit.

9.2.15 Follow-up Visit

This visit is required for patients who withdraw from the study or complete treatment but do not wish to continue to use GWP42003-P. The Follow-up visit will be performed 4 weeks (+ 3 days) after the patient's last dose of GWP42003-P (including final taper period dose) and can be conducted over the telephone. During this visit/call, caregivers will be asked for information on AEs, epilepsy-related hospitalizations, concomitant medications and/or changes to medication. The CWS/PCWS will also be administered.

9.2.16 Safety Telephone Calls

From Visit 3 until the 'End of Treatment' visit, safety telephone calls must be made every 4 weeks (\pm 7 days). In addition, during titration of doses above 20 mg/kg/day, safety telephone calls must be made every 7 days (\pm 3 days) until stable dosing is

achieved. All safety telephone calls will assess AEs, epilepsy-related hospitalizations, concomitant medications and/or changes to medication.

A post-taper safety telephone call must also be made (see [Section 9.2.14](#)).

10 WITHDRAWAL

In accordance with the Declaration of Helsinki⁷³, the FDA regulations relating to good clinical practice (GCP) and clinical trials^{74,75,76}, the EU Clinical Trials Directive 2001/20/EC⁷⁷ and/or other applicable regulations, a patient has the right to withdraw from the study at any time and for any reason without prejudice to his or her future medical care by the physician or at the institution.

The patient must be withdrawn from the study if any of the following apply:

- Administrative decision by the Investigator, GW, or a Regulatory Authority.
- Pregnancy.
- Protocol deviation that is considered to potentially compromise the safety of the patient.
- Withdrawal of patient consent/assent.
- Withdrawal of parent(s)/legal representative consent.
- Lost to follow-up.
- ALT or AST > 3 × ULN **and** (TBL > 2 × ULN **or** INR > 1.5).
- ALT or AST > 3 × ULN with the appearance of fatigue, nausea, vomiting, right upper quadrant pain or tenderness, fever, rash, and/or eosinophilia (> 5%).
- ALT or AST > 8 × ULN.
- ALT or AST > 5 × ULN for more than 2 weeks.

Note: Prior to withdrawal for the transaminase elevations noted above, the Investigator may choose to confirm the transaminase elevations by repeating the following laboratory tests within 24 to 48 hours: ALT, AST, TBL, INR, % eosinophils, gamma glutamyl transferase and alkaline phosphatase. **Should the above transaminase elevation criteria be confirmed, the patient must be withdrawn from the trial.**

Patients may also be withdrawn from the study for any of the following:

- Patient non-compliance.
- AE which, in the opinion of the Investigator, would compromise the continued safe participation of the patient in the study.
- Any evidence of drug abuse or diversion.
- Suicidal ideation or behavior of type 4 or 5 during the treatment period, as evaluated with the C-SSRS.

Should a patient request or decide to withdraw from the study, all efforts must be made to complete and report the observations as thoroughly as possible up to the date of withdrawal. Patients who withdraw should have their dose of IMP tapered gradually (10% each day) over a period of 10 days, beginning at the time the decision is made to discontinue. In some cases, tapering the dose of IMP may be inadvisable (e.g., continued dosing is not possible due to an AE). The decision on whether or not to taper IMP will be left to the Investigator's clinical judgment. All assessments required at the 'End of Treatment'/Withdrawal visit should be conducted if possible. If the tapered dose is administered, patients should continue to complete the IVRS and paper diary and return for the 'End of Taper Period' visit, if possible. For patients who begin to taper IMP but subsequently withdraw, the 'End of Taper Period' assessments (including ECG and clinical laboratory sampling) should be conducted, if possible; this visit should occur on the final day of dosing or as soon as possible after this date. Patients withdrawing due to an AE should be followed up according to [Section 12.7](#) safety follow-up visit. All information should be reported on the applicable CRF pages (refer to [Section 9.1](#)). Wherever possible, the safety follow-up visit should take place 4 weeks from the date of the last dose of IMP (refer to [Section 9.2.15](#)).

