If an unacceptable AE develops at any time during titration, dosing should initially be suspended or amended, at the Investigator's discretion, as appropriate, until the event has resolved or is well tolerated. During the maintenance period, Investigators may decrease the dose if a patient experiences intolerance, or increase the dose if required for better seizure control, until the optimal dose is found. The Investigator may schedule additional clinic visits during the maintenance period to facilitate dose adjustments, e.g., when increasing doses above 20 mg/kg/day. Patients whose dose has been decreased can have their dose increased again provided there is adequate tolerance. Dose increases above 20 mg/kg/day are recommended to be done slowly, with maximum increments of 2.5 mg/kg every 5–7 days. The maximum dose patients can receive will be 30 mg/kg/day.

For patients who do not immediately continue to use GWP42003-P following the 'End of Treatment' visit, IMP will be down-titrated at home (10% per day for 10 days). Additional IMP will be dispensed, if required. Patients who withdraw early should also begin the taper period following the Withdrawal visit (unless continued dosing is not possible due to an AE). The IVRS will generate the patient's daily IMP dosing volumes for the 10-day taper period, during which time IVRS and diary information will continue to be recorded.

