4. STATISTICAL METHODS

4.1 General Considerations

All tables will be presented by indication (where appropriate), including an overall count, as follows:

Dravet Syndrome (N=XX)	Lennox-Gastaut Syndrome (N=XX)	Overall (N=XX)
------------------------	--------------------------------	----------------

In all tables, listings and figures, the study visits will be referred to and labelled as per [Table 2](#)

Table 2 Study Visits

Actual Visit	Visit Label
Visit 1: Day 1	Day 1
Visit 2: Day 15	Day 15
Visit 3: Day 29	Day 29
Visit 4: Day 85	Day 85
Visit 5: Month 6 or Week 24	Week 24
Visit 6: Month 9 or Week 38	Week 38
Visit 7: Week 48 or End of Treatment (only patients who completed at 1 year)*	Week 48
Visit 8: Week 76	Week 76
End of Treatment (only patients who completed on or after Day 400)*	End of Treatment

End of Treatment (withdrawn patients only)	End of Treatment
End of Taper	End of Taper
Post-Taper Safety Call	Post-Taper Safety Call
Safety Follow-Up	Safety Follow-Up

* For some patients, the end of treatment visit occurs after one year in the OLE, whereas for other patients the end of treatment visit occurs after two or more years in the OLE.

Unless stated otherwise, continuous variables will be summarized showing the number of non-missing values (n), mean, standard deviation, median, minimum and maximum and categorical variables will be summarized showing the number and percentage of patients falling in each category. For continuous summaries of seizure frequency, the lower and upper quartiles will also be presented.

Minimum and maximum values will be presented to the same decimal precision as the raw data. Mean and median will be presented to one more decimal place than the raw data, and standard deviation to 2 more decimal places than the raw data. Percentages will be presented to one decimal place.

For patients who enter the OLE on the same day as the core study end of treatment or end of taper visit, the CRF for this study did not require some data to be entered for a second time. Hence, for visit based endpoints, if a patient does not have data entered in this study at Visit 1, then data from the end of treatment or end of taper visit in the core study will be used, provided that the date of collection is on Day 1 of the OLE.

Unless otherwise stated, all summaries will be presented by indication.

All analyses and summaries will be produced using SAS Version 9.4.

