4.1.4.2 Last Visit

Last visit for endpoints assessed at clinic visits is defined as the last scheduled visit (not including the end of taper or safety follow-up visits) at which patient's last evaluation is performed.

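### The protocol gives two start points for an early withdrawer's taper, so the SAP's End of Treatment row can mix full-dose results with results taken mid-taper or off drug

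*Protocol*

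**What the plan says.** **Taper start.** Protocol Section 10 ties the start to the decision: "tapered gradually (10% each day) over a period of 10 days, beginning at the time the decision is made to discontinue". Section 9.2.12 ties it to the visit: "Patients who withdraw early should also begin the taper period following the Withdrawal visit". Section 8.1.2 and the synopsis repeat the Section 9.2.12 rule. All of them allow the taper to be skipped, for instance when an adverse event prevents further dosing.

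**Taper rate.** Section 8.1.2: "IMP will be down-titrated at home (10% per day for 10 days"). Section 10 gives the same rate and length.

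**Timing of the Withdrawal visit.** Section 9.2.12 places it at the end of the maximum treatment period "or following early withdrawal from the study", with no limit on the days since the decision. Section 10 asks for that visit's assessments only where possible.

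**Timing of the End of Taper visit.** Section 9.2.13: "This visit will take place 10 (+ 3) days after the" End of Treatment or Withdrawal visit. It is the first scheduled CWS/PCWS assessment in the extension study (Appendix 1).

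**SAP.** Table 2 in SAP 4.1 has a row "End of Treatment (withdrawn patients only"), labelled End of Treatment. Patients who completed on or after Day 400 carry the same label. End of Taper is a separate row. SAP 4.1.4.2 defines a Last Visit, "not including the end of taper or safety follow-up visits".

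**The concern.** Table 2 keeps End of Treatment apart from End of Taper, which suggests that the first should describe patients still on their treatment dose and the second those who have come down. That separation works only if the Withdrawal visit precedes the taper. Under Section 10 it need not, and the SAP sections on visit-based endpoints never compare the visit date with the last full dose.

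Changes in laboratory values, ECG and vital signs are part of the primary safety endpoint. Patients who withdraw include those meeting the mandatory liver criteria and those leaving because of an adverse event, so they plausibly carry abnormal on-drug values. Results taken after dose reduction may be milder, and pooling them with completers' full-dose results blurs what the row means.

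ECG and laboratory tests are also done at End of Taper for early withdrawers who taper. If the Withdrawal visit already falls in the taper, the before-and-after comparison for those patients is lost. The withdrawal scales are affected too: the CWS asks about the last 24 hours, so its value at End of Taper depends on how long ago dosing stopped.

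**Working it through.** The plan gives no figure to reproduce, so the check compares the two rules and then illustrates their effect.

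**Where the rules agree and differ.** Let g be the days from the decision to the Withdrawal visit. If g = 0 the rules coincide. If g > 0, Section 10 has the patient tapering before the visit, while Sections 8.1.2 and 9.2.12 keep the patient on the treatment dose until it. Section 9.2.13 fits only the second rule. The documents give no value or upper limit for g, so every g below is an assumption.

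**Dose left at the Withdrawal visit under Section 10.** The documents do not say whether the first taper day is 90% or 100% of the dose, so both are shown:

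- first day at 90%: max(0, 100 − 10 × (g + 1))
- first day at 100%: max(0, 100 − 10 × g)

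**Delay to the End of Taper visit.** If the taper starts on the decision day, its tenth day is decision day + 9. The End of Taper visit falls g + 10 to g + 13 days after the decision. The delay after the last taper day is therefore g + 10 − 9 = g + 1 to g + 13 − 9 = g + 4 days.

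| Assumed gap g (days) | Dose left at Withdrawal visit | End of Taper visit, days after last taper day |
|---|---|---|
| 0 | 90–100% | 1–4 |
| 3 | 60–70% | 4–7 |
| 5 | 40–50% | 6–9 |
| 7 | 20–30% | 8–11 |
| 9 | 0–10% | 10–13 |
| 10 | 0% | 11–14 |

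At g = 10 the first CWS/PCWS overlaps in time with an assessment two weeks (± 3 days, so 11 to 17 days) after final dosing, which Section 9.2.14 treats as a separate contact.

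**Which SAP outputs depend on the visit row.**

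- Dependent: mean changes by visit for laboratory, ECG and vital signs; laboratory shift tables; by-visit counts of clinically significant vital-sign changes; CWS/PCWS at End of Taper.
- Not dependent: potential Hy's Law cases (any occurrence after Visit 1, SAP 4.5.3.1); flagged vital signs and ECG values (any post-baseline occurrence, SAP 4.5.8.1 and 4.5.8.2); adverse events.
- Hardly dependent: C-SSRS, which asks about the time since the last assessment (Protocol 9.1.11.5) and for which Protocol 13.6.2.4 counts the taper as part of the treatment period.

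**The case against.** The strongest reply is that the protocol's mechanics run through the Withdrawal visit. The IVRS generates the taper volumes, sites give it taper and termination information at clinic visits (Section 9.1.10), and extra taper supply is dispensed at the Withdrawal visit. If the decision is made there, nothing goes wrong. This makes small gaps plausible, but it does not remove Section 10's wording or set a limit on the gap.

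Several stronger readings are tempting and not supported:

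- **That most or all early withdrawers are affected.** Visits up to 28 weeks apart might suggest it, but nothing makes a patient wait for the next scheduled visit. Only those who taper, attend the visit and have a gap between decision and visit are affected.
- **That a head count can be given.** An assumed 20–40% withdrawal rate on 680 patients gives 136–272, but the documents state no rate, and all early withdrawers are the wrong denominator.
- **That safety signals would be hidden.** The any-occurrence counts stand. Transaminase elevations that trigger withdrawal are measured beforehand, with repeat tests at 24 to 48 hours, and abnormal laboratory values are listed separately.
- **That Last Visit results are distorted.** The SAP defines the term, but none of its endpoint sections or table titles uses it.

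It is also fair to say that the SAP never calls the row on-treatment; that is an inference from the separate End of Taper row. Patients who stop abruptly for an adverse event can be off drug at this visit under either rule, so reconciling the taper start would not remove every off-drug result. CWS/PCWS is also repeated at the post-taper call and at follow-up, so the withdrawal assessment does not rest on one visit.

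**Conclusion.** The contradiction is literal and the sections must be reconciled. Its effect on the analysis is possible rather than certain, and modest: it can blur one visit row's mean changes, laboratory shifts and by-visit vital-sign counts, and it shifts the first CWS/PCWS, in a descriptive study without hypothesis tests. For an affected patient the dose could be anywhere from nearly full to zero, depending on an undocumented gap. The illustration assumes that the taper starts on the decision day and runs its full 10 days. The number of such patients cannot be computed from the documents. The point is worth correcting because the remedy is cheap, not because the safety conclusions turn on it.

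**What to change.** **Protocol.** The sponsor should reconcile Section 10 with Sections 8.1.2, 9.2.12 and 9.2.13 and the synopsis, so that one rule fixes the taper start relative to the Withdrawal visit. Which rule is a clinical matter for the sponsor.

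**SAP 4.1, Table 2.** Flag withdrawn patients' End of Treatment results collected after the last pre-taper dose, using the last treatment-phase dose date that SAP 4.5.8.13 already takes from the CRF. State that, if the taper began before the visit, this date means the last dose before the first reduction; the daily paper diary (Protocol 9.1.12) can confirm it. Present the row with and without the flagged results. Showing both matters, because simply removing them would drop patients who stopped for an adverse event.

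**SAP 4.5.8.5 and 4.5.8.6.** Report End of Taper CWS/PCWS by days since last dose, from the final dose date recorded at that visit.

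**Cost.** A protocol clarification, a few SAP sentences, one extra summary split and a smaller n in the restricted row. No new data are needed.
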